11.4 Missing Data

For the primary endpoint, minimal or no missing data is expected. Missing primary outcome will be assumed missing at random and excluded for analyses. However, if more than 5% of primary endpoint is missing, multiple imputation technique will be applied followed by sensitivity analyses. All the other measurements will be analyzed accordingly with all available data using a complete case approach.

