7.5.2 Secondary Endpoints

- Numeric rating scale (NRS) for pain experienced during study procedure balloon inflations
- Procedural cost
- Procedure times
- Maximum balloon pressure
- Device success
- Safety measures, including rupture, circumferential tears, and reintervention/patency

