7.5.3 Additional Measures

- Anatomic success
- Clinical success
- Adverse events (refer to Section 9.6: Adverse Events for a list of reportable events)
- Primary patency through 90 days

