10.0 Participation Endpoints of the Study

A patient's participation in the study will end after any of the following:

- Patient withdrawal (patient- or investigator-initiated)
- Medical records determined to be unobtainable for chart review
- Early termination of the study
- Patient death
- Completion of 90-Day chart review

After a patient exits the study for any reason (e.g., withdrawal, records determined to be unobtainable, study closure, or study completion), no additional data will be collected. Information up to the date of the participation endpoint will be provided to the Sponsor during the 90-Day chart review.

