11.3.2 Analysis of secondary endpoints

Differences in pain, procedural costs, procedure times, and maximum balloon pressure will be assessed overall by one-sided t-tests, with Enforcer balloon having favorable outcomes. In addition, regression models will be used to incorporate the stratification factors as covariates and reported if found to be significant. If the parametric assumptions are not met, nonparametric methods will be used. The safety claim will be evaluated with a Z-statistic, with a non-inferiority of Enforcer balloon at a margin of 10%. The observed non-inferiority margin will also be presented.

Adjustments for multiplicity will be made using the Holm procedure to control the family-wise error rate to 0.05 across the family of secondary endpoints.

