11.3.3 Analysis of additional measures

The same analysis strategies will be applied to the additional measures. For continuous measures, the difference between the two treatment groups will be assessed by t-test statistics. The impact of the two stratification variables on the outcomes between the two groups will also be explored, and reported if the test suggests a difference. If the parametric assumptions are not met, nonparametric methods will be used. Survival analysis techniques such as Kaplan-Meier or Cox Proportional Hazards will be incorporated if censoring of data occurs.

Key components of the additional measures may also be compared, including specific adverse events associated with the procedure, such as vessel rupture or tear.

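### Reintervention/patency is listed under two endpoint tiers, but survival methods are provided only for the additional measures, so the complete-case rule in 11.4 is left to govern patency in the safety test

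*Combined protocol and SAP*

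**What the plan says.** Patency appears in two endpoint tiers. Section 7.5.2 lists among the secondary endpoints "Safety measures, including rupture, circumferential tears, and reintervention/patency". Section 7.5.3 lists among the additional measures "Primary patency through 90 days".

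Each tier has its own analysis text:

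- Section 11.3.2 (secondary): "The safety claim will be evaluated with a Z-statistic, with a non-inferiority of Enforcer balloon at a margin of 10" percent. It names no estimator and no method for censored follow-up.
- Section 11.3.3 (additional): "Survival analysis techniques such as Kaplan-Meier or Cox Proportional Hazards will be incorporated if censoring of data occurs".

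Section 11.4 then covers missing data. For the primary endpoint, "if more than 5% of primary endpoint is missing, multiple imputation technique will be applied followed by sensitivity analyses". For the rest, "All the other measurements will be analyzed accordingly with all available data using a complete case approach". It makes no exception for time-to-event outcomes.

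Incomplete 90-day follow-up is foreseen. Section 10.0 ends participation at withdrawal, death, early termination, or "Medical records determined to be unobtainable for chart review". Partial follow-up is nevertheless collected: "Information up to the date of the participation endpoint will be provided to the Sponsor during the 90-Day chart review". Under the Appendix D definition, primary patency is lost only when restenosis or occlusion leads to reintervention or abandonment. A patient who dies or withdraws with a working circuit is therefore censored and is not counted as a failure.

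**The concern.** One outcome sits under two rules, and nothing says which governs. Read as an additional measure, patency gets survival methods. Read as part of the secondary safety claim, it gets a Z-statistic whose estimator is not named, with the complete-case sentence in 11.4 as the only instruction on incomplete follow-up.

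The natural way to apply that sentence to a yes/no 90-day outcome is lopsided. A patient who fails on day 30 and then leaves has a known outcome and stays in. A patient who is failure-free on day 60 and then leaves has no day-90 outcome and is removed. Failures are kept and successes are lost, so the failure proportion rises. It rises more in an arm with more exits. The follow-up that Section 10.0 takes care to collect on these patients goes unused.

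At stake are the patency component of a non-inferiority comparison, the agreement between two reported figures for the same outcome, and a choice of estimator that could still be made after the data are seen.

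**Working it through.** **Plan figures.** The documents give no sample size, power or exit rate for patency or for the safety claim, so there is no plan figure on this point to reproduce. The 250-lesion calculation concerns the primary endpoint and is not involved.

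**Inputs**

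- 90-day patency of 62.0%, the pilot Kaplan-Meier estimate in Section 5.0. True failure is then 38%.
- About 100 patients per group (Section 11.1).
- Assumed: 5% to 20% of patients have an exit time before day 90; constant hazard of patency loss; exits spread evenly over the 90 days and independent of patency.

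**Formulas.** Take 90 days as the time unit and let c be the exit fraction.

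- Hazard: L = −ln(0.62) = 0.478.
- Chance that a patient with an early exit time fails before it: p = 1 − 0.38/L = 1 − 0.795 = 0.205.
- Observed failures: E = (1 − c) × 0.38 + c × p.
- Known failure-free at day 90: F = (1 − c) × 0.62.
- Dropped: D = c × (1 − p).
- Complete-case failure = E/(E + F).

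At c = 0.20: E = 0.304 + 0.041 = 0.345; F = 0.496; D = 0.159; complete-case failure = 0.345/0.841 = 41.0%.

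| Assumed exits | Complete-case failure | Excess over 38% | Patients dropped |
|---|---|---|---|
| 5% | 38.7% | 0.7 points | 4% |
| 10% | 39.4% | 1.4 points | 8% |
| 15% | 40.2% | 2.2 points | 12% |
| 20% | 41.0% | 3.0 points | 16% |

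**Sensitivity to the model.** With exponential instead of uniform exit times, the excess is 0.7, 1.4, 2.1 and 2.9 points. With true patency of 80%, it runs from 0.4 points at 5% exits to 2.0 points at 20%.

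**Kaplan-Meier on the same data.** In 5,000 simulated arms of 100 patients with exponential exits, mean 90-day Kaplan-Meier patency is 62.1%, 62.0% and 61.9% at 5%, 10% and 20% exits. It is essentially unbiased against the true 62%.

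**Between arms, equal true patency**

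- Equal exits: the two biases cancel and the difference is unbiased.
- 5% versus 15% exits: 40.2 − 38.7 = 1.5 points of spurious difference.
- 5% versus 20% exits: about 2.4 points (41.02 − 38.66).

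**Between arms, equal exits but unequal patency.** At 20% exits with true patency of 62% and 80%, complete-case failures are 41.0% and 22.0%. The difference is 19.0 points against a true 18.0, a distortion of about 1 point.

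**The other meaning of complete case.** If every patient whose follow-up would not have reached day 90 is removed, including those who failed earlier, the retained patients are a random subset under independent censoring. Their failure proportion is still expected to be 38%. There is no bias, but observed events and follow-up time are lost.

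**The case against.** Four points can be made for the plan.

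- **A Z-statistic need not be a binary test.** A difference in Kaplan-Meier estimates divided by its Greenwood standard error is also a Z-statistic. A reader might infer that 11.3.2 prescribes a biased test. It does not: it is silent on the estimator. It also leaves open whether the 10% margin applies to a composite, to each safety item or to some of them. Rupture and tears are procedural and barely touched by censoring. This stands, and it limits the point to the patency component.
- **Section 11.4 can be read kindly.** It speaks of all available data, and complete case may be meant only as the contrast to multiple imputation. Section 11.3.3 is the more specific text on censoring and opens by carrying the same strategies across. That may settle patency as an additional measure. It does not reach the safety test, because the censoring sentence is placed only under 11.3.3, and 11.4 as written excludes nothing but the primary endpoint.
- **The effect is small and rests on assumptions.** The documents give no exit rate, follow-up is a chart review without a study visit, and the 62% comes from 28 patients with fistulas at one center. With 100 per arm, the standard error of the difference is √(2 × 0.62 × 0.38/100) = 6.9 points, so 1.5 points is about 0.2 standard errors. A reader might infer that differing exits will by themselves produce or hide a safety difference. Nothing in the documents suggests that exits will differ by arm, and with equal exits and equal patency the bias in the comparison is zero. This stands as to size.
- **Kaplan-Meier is not automatically right.** Death ends participation but is not a patency event, so censoring at death may be informative. This also stands and belongs in the fix.

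None of this removes the gap: one outcome, two rules, and no statement of which applies.

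**Conclusion.** The point holds as a conflict of rules with a modest numerical consequence. No bias in the formal safety test has been shown.

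If complete case keeps early failures and drops failure-free early exits, 90-day failure is overstated by about 0.7 to 3 points per arm and 4% to 16% of patients are discarded. That rests on assumed exits of 5% to 20%, the pilot's 62% patency, constant hazard and independent censoring. The comparison between arms is biased only if exits or true patency differ by arm. More exits in the Enforcer arm would count against it in the non-inferiority test, and more in the control arm would favor it. On the stricter meaning of complete case, the loss is one of information only.

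The change should still be made. The stated rule can give a worse answer than a method the plan already names, and correcting it costs almost nothing. The primary endpoint and its sample size are unaffected.

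**What to change.** - In 11.4, exempt reintervention/patency and any other time-to-event outcome from the complete-case rule, and state that follow-up to the exit date is used with censoring at exit.
- In 11.3.2, base the patency component of the non-inferiority Z-statistic on the between-arm difference in 90-day Kaplan-Meier estimates with Greenwood standard errors. Say which safety items the 10% margin covers.
- Use that estimator wherever patency is reported, so that the secondary and additional results agree.
- Leave rupture and circumferential tears on the simple Z-test.
- Report the number and timing of exits by arm and by reason, with deaths shown separately, because Kaplan-Meier assumes non-informative censoring.

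The cost is a few sentences in the analysis section. No new data are needed, since exit dates and information up to exit are already to be collected. The one downside is the reliance on non-informative censoring, which reporting deaths by arm exposes but does not remove.

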11.5 Site-level Poolability

This is a multi-center study with up to 10 clinical sites. It is not intended to incorporate study sites into primary endpoint analyses. However, the primary endpoint will be examined across sites and reported if necessary.

12.0 Deviations from Study Plan

Except under emergency situations when necessary to preserve the rights, safety, or well-being of study patients, principal investigators are not allowed to deviate from this study plan without documented prior approval by:

- the sponsor; and
- the IRB

Clinical study noncompliances (i.e., deviations from the study plan, investigator agreement, IRB policy, and/or any applicable regulations/standards) will be documented, along with an explanation and corrective and preventive actions, and reported to the sponsor.

The principal investigator-required notifications/reports are described in Table 12.0-1. The reports will be provided as required by the study plan, IRB policies, or local regulations, whichever is more stringent.

Table 12.0-1. Clinical Study Noncompliance Reports

Report	To	Timeframe to submit report (upon awareness)
Deviation to protect the life or physical well-being of a patient in an emergency	Sponsor IRB	As soon as possible, but no later than 5 working days
Deviation that affects the scientific soundness of the clinical study	Sponsor IRB	Within 5 working days
All clinical study noncompliances	Sponsor IRB, if required per local policy	15 working days

The sponsor is responsible for reporting clinical study noncompliances to the reviewing IRB(s) and investigator(s) as required according to applicable regulations/standards.

In accordance with applicable regulations/standards, the sponsor will review all clinical study noncompliances and take suitable action(s) to secure compliance. If appropriate, based on the number and nature of noncompliances, actions may include discontinuation of device shipment and/or termination of a principal investigator's participation in this clinical study.

13.0 Data Collection and Management

Patient data will be documented and recorded by trained personnel at the clinical site onto eCRFs through an EDC system. This is a secure, validated, web-based system, allowing those with permission to access data from any location at any time. Source data must be retained for all data entered into the EDC system. The patient-reported pain assessment and the physician assessment of the quality and performance of the study product may be directly entered into the EDC system.

Clinical site personnel are required to undergo training and will have unique login names and passwords in order to enter patient data. In accordance with 21 CFR Part 11, the EDC system creates a secure, computer-generated, time stamped audit trail to record the date and time of operator entries and actions that create, modify, or delete electronic records. Principal investigators will review and electronically sign the eCRFs to confirm that the data recorded are accurate and complete.

Principal investigators will provide all applicable clinical data and documentation to the sponsor in a timely manner. All clinical study documents (including patient data) must be retained as required by the applicable regulations/standards. The principal investigator or

clinical site personnel are requested to contact the sponsor before removing any documents pertaining to the clinical study. The sponsor is responsible for database management, data verification, data archiving, and data retention.

As needed to assist the sponsor in its research (e.g., during evaluation of an adverse event), data will be accessible to the sponsor, the participating principal investigators, the manufacturer, and companies or individuals the sponsor authorizes.

14.0 Monitoring

The conduct of the clinical study will be supervised through a process of centralized, remote, and on-site monitoring.

The sponsor will perform centralized monitoring (i.e., data review) throughout the study for adverse events, unexpected results, and for data completeness, consistency, and clarity. A formal query process in the EDC system will be utilized to resolve data discrepancies. Queries may arise from automated processes or from manual review of eCRFs, procedural reports, imaging data, or correspondence received. Principal investigators will ensure timely resolution of queries.

On-site monitoring will be implemented as necessary throughout the course of the study to ensure the principal investigators are fulfilling the obligations set forth in the study plan, agreement(s), IRB policies, and applicable regulations/standards. Source data verification will be performed during on-site visits. If allowed per site policy, some source data verification may be done remotely, according to the monitoring plan. The principal investigator and clinical site will provide direct access to source data/documents for study-related monitoring, audits, IRB review and regulatory inspection. Standard practices for monitoring the study are summarized in Appendix C.

15.0 Clinical Study Administration

15.1 Approvals

The principal investigator is responsible for obtaining approval of this clinical study (including the study plan, informed consent form, and all patient materials) from the relevant IRB at their associated clinical site. The clinical study will not begin at a particular clinical site until a favorable opinion of the IRB has been obtained. The study plan and other clinical study documents may be revised by the sponsor, as appropriate,

based on new or changes to important information. A summary of the study plan revision history will be documented by the sponsor. Changes or modifications to the study plan, informed consent form, or patient materials may not be initiated without IRB approval. The principal investigator is responsible for keeping their IRB informed as to the progress of the study and complying with requirements imposed by their IRB. Furthermore, the sponsor and the principal investigator will ensure that local regulations concerning data protection are followed.

15.2 Clinical Study Reporting

Principal investigators will provide the notifications/reports described in Table 15.2-1. The reports will be provided as required by IRB policies.

Table 15.2-1. Clinical Study Reports

Report	To
Withdrawal of IRB approval	Sponsor
Progress report	IRB
Final report	IRB

The sponsor is responsible for providing progress reports and final reports, notification of study completion or termination, and reporting significant findings to the reviewing IRB(s) and principal investigator(s) as required according to applicable regulations/standards.

15.3 Contact information

Refer to Appendix A for a list of the sponsor, monitor, and manufacturer. Contact information and qualifications for the clinical site(s), principal investigator(s), or other institutions involved, will be maintained by the sponsor. The sponsor will also maintain contact information for each reviewing IRB.

15.4 Insurance

Insurance for the study will be obtained by the sponsor prior to patient enrollment.

16.0 Publication Policy

This clinical study will be registered on www.ClinicalTrials.gov and the intent is to make study results public. Publication policy, rights, and obligations for this study will be

negotiated, detailed, and defined in the clinical study's contractual documents with the clinical site and principal investigator.

APPENDIX B: Schedule of Events

	Pre-procedure	Procedure	Follow-up
			90 days
Informed consent	X		
Demographics	X		
Medical history	X		
Physical exam	X		
Baseline angiography	X		
Randomization		X	
Angioplasty		X	
Completion angiography ^a		X	
Patient-reported Pain Assessment		X	
Chart Review			X
Adverse events		X	X ^b

^a Completion angiography should be performed after treatment with the Enforcer or conventional angioplasty balloon. If an adjunctive procedure is performed, an additional angiography should be performed after completion of that procedure.

^b Events with an onset date after 90 days post-procedure will not be collected.

APPENDIX C: Standard Practices for Monitoring

1.0 Selection of the monitor

Designated by the sponsor to oversee the clinical study, the monitor may be an employee of Cook, an employee of a Contract Research Organization (CRO), or an independent contractor or consultant. The monitor will be qualified by training and experience and will be familiar with the clinical study product(s), study plan, and applicable regulations/standards.

2.0 General duties of the monitor

Clinical sites will be monitored throughout the clinical study to verify:

- The protection of the rights, safety, and welfare of patients;
- The clinical study is being conducted in accordance with the study plan, agreement(s), IRB policies, and applicable regulations/standards;
- The proper use of the clinical study product;
- Adverse events and clinical study noncompliances are reported; and
- The quality and integrity of the clinical study data.

2.1 Initiating the study

Prior to enrolling a patient, the monitor and/or sponsor representative will participate in a site initiation visit with each clinical site.

At a minimum, the following will be addressed with the principal investigator and appropriate clinical site personnel:

- Training on responsibilities and requirements per the study plan, agreement(s), and applicable regulations/standards; and
- The IRB approval letter and approved informed consent are on file prior to initiation of the clinical study.

2.2 Periodic visits

During the course of the study, the monitor may visit the clinical site to ensure that the obligations set forth in the study plan, agreement(s), IRB policies, and applicable regulations/standards are fulfilled. The frequency of site visits may vary and the following activities will be performed as needed during the course of the study:

- Perform source data verification per the monitoring plan
 - Ensure the reviewed information recorded in the eCRFs is complete, accurate, and legible.
 - Review patient charts for adverse events and ensure that events are appropriately reported.
 - Ensure the reasons for patient(s) failing to complete the study are documented.
- Review Investigator File (e.g., essential documents)
 - Verify that there is a signed/dated informed consent document for each patient enrolled to date and confirm that the correct version of the informed consent was signed and dated prior to performing any study-related procedures.
 - Ensure applicable version of the study plan and agreements are being followed and any changes to the study plan, informed consent form have been approved.
 - Ensure accurate, complete, and timely reports have been made to the sponsor and IRBs if applicable.
 - Ensure the appropriate training records are on file if the Signature and Delegation of Responsibilities Log at the clinical site has been updated.

2.3 Close-out visits

Close-out visits may be conducted via an on-site or telephone call to ensure, at minimum:

- Reviewed data are accurate and complete or a justification has been provided for any missing data
- All previously identified follow-up items and clinical study non-compliances have been reported and resolved, if applicable
- All essential documents have been filed at the clinical site
- The principal investigator understands their obligations regarding documentation and retention requirements.

